11.0 Risks and Benefits	17
11.1	17
Physical, Functional, Range of Motion Testing	17
11.2 Blood Flow Restriction device	17
11.3 DEXA Scan	18 17
11.4 InBody Bioelectrical Impedance scan	18
11.5 Confidentiality	18
11.6 Data Safety Monitoring Plan	18
12.0 Ethical Considerations.....	18
13.0 References	19

Use of Blood Flow Restriction + Standard of Care Physical Therapy to Improve Functional Outcomes after
Anterior Cruciate Ligament Reconstruction
PI: [name].
Institution: UAMS
Sponsor: UAMS

List of Abbreviations

ACL	Anterior cruciate ligament
BFR	Blood Flow Restriction
CRF	Case Report Form
DEXA	Dual-energy X-ray Absorptiometry
EMR	Electronic medical record
FDA	Food and Drug Administration
IRB	Institutional Review Board
MVC	Maximal voluntary contraction (of the quad muscles)
NIH	National Institutes of Health
PBFR	Personalized Blood Flow Restriction
PT	Physical Therapist
RIOA	Reynolds Institute on Aging
ROM	Range of Motion (of the knee joint)
UAMS	University of Arkansas for Medical Sciences
UPIRTSO	Unexpected problem involving risks to subjects or others

Study Schema

Surgeon collaborators or their designees screen their orthopedic clinic for eligible subjects and send referrals to study staff via UAMS email.

Study staff contact referrals via phone or email to discuss consent process.

Visit 1: Subjects come to RIOA for informed consent process prior to surgery.
Randomization (1:1) occurs.

Visit 2: Approx. 7-10 days prior to surgery, subjects come to RIOA for baseline testing.

Subjects undergo scheduled knee surgery at UAMS

***Prescribed physical therapy begins with or without BFR per randomization at UAMS
Colonel Glenn facility***

Visit 3: Subjects come to RIOA for post-operative testing approx. 8 weeks postop.

Prescribed physical therapy continues with/without BFR per randomization

Visit 4: Approx. 12 weeks postop, subjects come to RIOA for mid-point testing.

Visit 5: Approx. 16 weeks postop, subjects come to RIOA for end-point testing.

Use of Blood Flow Restriction + Standard of Care Physical Therapy to Improve Functional Outcomes after
Anterior Cruciate Ligament Reconstruction
PI: [name].
Institution: UAMS
Sponsor: UAMS

Study Calendar

Procedure	Visit 1	Visit 2	Visit 3	Visit 4	Visit 5
Informed consent	X				
10-meter walk test		X	X	X	X
bilateral MVC		X	X	X	X
DEXA scan		X	X	X	X
In Body scan		X	X	X	X
Stair ascent			X	X	X
Stair descent				X	X
Y-balance test			X	X	X

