10.0 Data Analysis, Use and Handling

10.1 Statistical Analysis/Power Calculations

Descriptive statistics for numeric outcome measures as well as demographic and clinical characteristics will be reported as means and standard deviations or medians and interquartile ranges, as appropriate. For each strength and functional outcomes, the difference between the two groups by the mid-point and final visit will be tested with two-sided hypotheses at a significance level of 0.05. For each parameter, an analysis of

Use of Blood Flow Restriction + Standard of Care Physical Therapy to Improve Functional Outcomes after
Anterior Cruciate Ligament Reconstruction
PI: [name].
Institution: UAMS
Sponsor: UAMS

covariance (ANCOVA) model will include terms for the main model effect of intervention group with pretest as a covariate for each parameter. For each group comparison, homogeneity of variances, normality, and parallel posttest-pretest slopes will be assessed. In the case of non-normal distributions, data transformations will be evaluated and applied if appropriate. Otherwise, for any group comparison with unmet ANCOVA assumptions, an alternative analysis such as generalized linear mixed models will be pursued instead. Statistical analysis will be performed using SAS version 9.4. The objective of this pilot work is to obtain adequate data on which to power future studies and project submissions.

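### The ANCOVA in Section 10.1 needs a pretest for every strength and functional outcome, but stair ascent, stair descent and Y-balance have no pre-surgery measurement, so the model cannot be fitted for them

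*Combined protocol and SAP*

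**What the plan says.** Section 10.1 sets one analysis for all strength and functional outcomes. "For each strength and functional outcomes, the difference between the two groups by the mid-point and final visit will be tested", two-sided at 0.05. The model is an ANCOVA with a term for intervention group, "with pretest as a covariate for each parameter". For each comparison, "homogeneity of variances, normality, and parallel posttest-pretest slopes will be assessed". If a transformation does not help, then "for any group comparison with unmet ANCOVA assumptions, an alternative analysis such as generalized linear mixed models will be pursued instead". Descriptive summaries are separate and will be "reported as means and standard deviations or medians and interquartile ranges, as appropriate".

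The Study Schema fixes the meaning of the visits:

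- "Visit 2: Approx. 7-10 days prior to surgery, subjects come to RIOA for baseline testing"
- "Visit 3: Subjects come to RIOA for post-operative testing approx. 8 weeks postop"
- "Visit 4: Approx. 12 weeks postop, subjects come to RIOA for mid-point testing"

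Visit 5, at about week 16, is the end-point. The Schema places the start of randomized therapy, with or without BFR, between surgery and Visit 3.

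Two other places define the pretest. Section 1.0 lists four data-collection occasions, of which the first is before surgery and the others are at weeks 8, 12 and 16. Section 2.1 speaks of a pre-test, a post-test and two further testing points during therapy. Together they make the pretest the pre-surgery visit, Visit 2.

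**The concern.** An ANCOVA needs a covariate value for each subject. If an outcome is not measured at Visit 2, its pretest does not exist. The model then cannot be fitted, and the check that posttest-pretest slopes are parallel has nothing to work on. The analyst must choose another model that the plan does not state, possibly after seeing the data. The usual candidates are no covariate, a different Visit 2 measure, or an early post-operative value of the same test.

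These do not estimate the same thing. A comparison without a covariate, or with a pre-surgery covariate, estimates the full effect of allocation. A value taken after therapy has begun may already carry part of that effect, and adjusting for it removes that part. Section 8.0 says BFR is used mainly early in rehabilitation, so some effect by week 8 is plausible.

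**Working it through.** **Step 1. Schedule against model.** The strength and functional rows of the Study Calendar are:

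| Outcome | First measured | Value at Visit 2? | Stated ANCOVA can be fitted? |
|---|---|---|---|
| MVC | Visit 2 | yes | yes |
| 10-meter walk | Visit 2 | yes | yes |
| Stair ascent | Visit 3 (week 8) | no | no |
| Y-balance | Visit 3 (week 8) | no | no |
| Stair descent | Visit 4 (week 12) | no | no |

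Section 5.0 agrees. Apart from body composition, its Visit 2 paragraph lists only strength testing of each leg and the walking test. For stair descent, the first value is itself the mid-point outcome.

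**Step 2. Count.** Three of five rows lack a pretest. Over two comparison visits that is 3 × 2 = 6 of 5 × 2 = 10 comparisons. Section 9.4 treats stairs as one test, which gives two of four tests. Counting legs or reach directions would give other totals. The list of affected outcomes does not change. DEXA and InBody have Visit 2 values and are not affected.

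**Step 3. Does other text close the gap?**

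- The fallback is triggered by unmet ANCOVA assumptions. A missing covariate is not a failed assumption. A mixed model could be fitted without a baseline, but the plan does not say that it will be, or in what form.
- Section 9.8 gives an order of tests for every visit and includes stairs and Y-balance. It sets sequence; it does not add tests to Visit 2 that both the calendar and Section 5.0 leave out.

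**Step 4. Cost of having no pretest.** The plan states no effect size, SD or power, so there is no figure of its own to reproduce. From the documents: a target of 20 completers (Section 4.0) randomized 1:1 (Section 7.0), so 10 per arm, and two-sided 0.05. Assumed: a true effect of 1 SD and a within-arm correlation r between covariate and outcome.

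- No covariate: noncentrality = 1/√(2/10) = 2.236 on 18 df, power 56.2%.
- True same-test pretest, r = 0.5: residual SD = √(1 − 0.25) = 0.866, on 17 df. Power is 65.8% by simulation (40,000 runs). The closed formula gives 68% because it ignores chance imbalance in the covariate.
- A different Visit 2 measure, by the same simulation: 53.7%, 55.3%, 57.4% and 61.0% at r = 0.1, 0.2, 0.3 and 0.4. It matches or beats no covariate only from about r = 0.3.

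**Step 5. If an analyst did use Visit 3 (conditional).** Let d be the true effect at the later visit and f the share of it already present at week 8. With equal SDs the ANCOVA slope is r, so the estimate is d − r × (f × d) = d(1 − rf). At r = 0.5 the share kept is 100%, 88%, 75% and 50% for f = 0, 0.25, 0.5 and 1. At r = 0.7 and f = 1 it is 1 − 0.7 = 30%. The documents give neither r nor f.

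**The case against.** The strongest reply is that the obvious response does no harm. An analyst who finds no pretest drops the term and compares the groups directly. Randomization makes that unbiased, and it is also the first option in the fix. This stands, and it limits the point to pre-specification. It does not remove it, because the plan states a different model and nothing commits the analyst to that step.

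A second reply is that this is a pilot meant to supply data for powering later studies, with no stated primary outcome or power target. That also stands in part. The descriptive summaries do not depend on the ANCOVA, so the planning data survive. But Section 10.1 also plans formal tests at 0.05, and Section 10.2 allows publication.

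Stairs and Y-balance may have been left out before surgery for the safety of the injured knee. The documents do not say so. It would explain the schedule without supplying an analysis.

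A reader might infer something stronger: that the plan leaves Visit 3 open as the pretest, and so invites a shrunken treatment effect. The documents do not support this. Sections 1.0 and 2.1 together make the pretest the pre-surgery visit and week 8 one of the additional points, and the Schema labels Visit 2 as baseline and Visit 3 as post-operative. Using Visit 3 would depart from the plan's own terms, and for stair descent there is no Visit 3 value.

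**Conclusion.** The point holds as an inconsistency between the schedule and the analysis text. For stair ascent, stair descent and Y-balance, the ANCOVA and its parallel-slopes check cannot be carried out, and no replacement is written. This rests on the documents alone and needs no assumed values; only the fraction depends on how outcomes are counted.

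The consequence is moderate. The tested comparison and its adjusted estimate are left undefined for these outcomes; the raw summaries and the analyses of MVC and walking speed are untouched. The power figures assume a 1 SD effect, 10 per arm and the stated correlations. The Visit 3 shrinkage is an illustration of a choice worth barring explicitly. It does not describe what the plan prescribes.

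**What to change.** Add to Section 10.1, for example:

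> Stair ascent, stair descent and Y-balance have no pre-surgery value. Groups will be compared on these outcomes at Visits 4 and 5 by the same linear model without a pretest term. Visit 3 values, and Visit 4 values of stair descent, are post-randomization and will not be used as covariates.

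If the team expects a within-arm correlation of about 0.3 or more, it may instead name one Visit 2 measure per outcome in advance, such as walking speed for stairs and surgical-leg MVC for Y-balance. The slopes check can then be applied to that covariate. A weaker substitute gains nothing.

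The cost is a short text amendment, which Section 12.0 requires to go through the IRB. No visit, test or data item is added. The downside is lower precision than a same-test pretest would give (about 56% against 66% power under the assumptions above). If BFR truly had no effect by week 8, barring Visit 3 would forgo about the same 10 points at r = 0.5.

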10.2 Dissemination of Data

Results of this study may be used for presentations, posters, or publications. The publications will not contain any identifiable information that could be linked to a subject.

10.3 Data Handling and Recordkeeping

Physical Therapy sessions will be documented by Physical Therapists in EPIC. Data will be transferred from EPIC to the UAMS data warehouse and then imported into REDCap so no mistakes are introduced between data collection and data analysis. Outcome testing data (without identifiers) will be entered into REDCap to facilitate analyses. These files are maintained on secure password-protected UAMS servers. Approximately 7 years after study completion, electronic records will be destroyed per UAMS disposal guidelines. At no time shall Protected Health Information be released to non-study personnel.

10.4 Data Access

All subjects will be assigned a unique identifying code or number. The key to the code (the instrument associating the data with subject identity) will be kept on a password-protected UAMS server. Only study staff members will have access to the code and information that identifies the subject in this study. This file will be deleted approximately seven years after data analysis is completed.

Use of Blood Flow Restriction + Standard of Care Physical Therapy to Improve Functional Outcomes after
Anterior Cruciate Ligament Reconstruction
PI: [name].
Institution: UAMS
Sponsor: UAMS

Epic medical record will be accessed by study staff to extract specific data from the PT notes for exercises performed, noting repetitions, sets, resistance, occlusion, pain level, Fear-Avoidance Beliefs questionnaire, and ROM measurements.

11.0 Risks and Benefits

There are no guaranteed benefits for the subjects, though there is some evidence that additional rehabilitation improves functional outcomes. Anticipated risks associated with this protocol are described in detail below. All experimental procedures will be performed by appropriately trained and credentialed personnel. The PI and/or study physician will be responsible for oversight of study procedures and evaluation of adverse events.

There are no known risks of answering the questions on the Fear and Avoidance Belief questionnaire that the Physical Therapy department uses.

11.1

Physical, Functional, Range of Motion Testing

The primary risks are fatigue and muscle soreness.

11.2 Blood Flow Restriction device

Possible adverse effects which may occur from performing blood flow restriction techniques using a pneumatic tourniquet include bruising at the site of the cuff, numbness, cold feeling, venous thrombus, fainting/dizziness, delayed onset muscle soreness, increased perceived exertion/pain/discomfort, stiffness, weakness, skin discoloration, exercise-induced rhabdomyolysis. Symptoms of tourniquet paralysis are motor paralysis and loss of touch, pressure, and proprioceptive responses. The physical therapists participating in the study have all demonstrated proficiency in the BFR approach.

Use of Blood Flow Restriction + Standard of Care Physical Therapy to Improve Functional Outcomes after
Anterior Cruciate Ligament Reconstruction
PI: [name].
Institution: UAMS
Sponsor: UAMS

11.3 DEXA Scan

Subjects will undergo four DEXA scans for whole-body composition. The radiation exposure for one DEXA scan is approximately equal to $\frac{1}{2}$ of the radiation from a chest x-ray.

11.4 InBody Bioelectrical Impedance scan

Subjects will undergo four of these scans. This machine (InBody770, BioSpace, Seoul, South Korea) is a widely used commercial device that is FDA approved and poses no risks.

11.5 Confidentiality

A potential risk to study subjects is the loss of confidentiality. Measures to protect the confidentiality of study subjects will be implemented as described in the Data Handling and Recordkeeping section above.

11.6 Data Safety Monitoring Plan

- Study staff will ask subjects about the occurrence of adverse events during study visits.
- Physical therapists will monitor for adverse events during intervention/rehab visits. These will be documented in their Epic notes.
- The PI and study physician are responsible for reviewing and evaluating adverse events.
- Adverse events will be recorded in the CRF and on an excel spreadsheet that is submitted to the IRB at required intervals.
- UPIRTSOs will be reported to the IRB within 24 hours of their discovery.

12.0 Ethical Considerations

Use of Blood Flow Restriction + Standard of Care Physical Therapy to Improve Functional Outcomes after
Anterior Cruciate Ligament Reconstruction
PI: [name].
Institution: UAMS
Sponsor: UAMS

This study will be conducted in accordance with all applicable government regulations and University of Arkansas for Medical Sciences (UAMS) research policies and procedures. This protocol and any amendments will be submitted and approved by the UAMS Institutional Review Board (IRB) to conduct the study.

The formal consent of each subject, using the IRB-approved consent form, will be obtained before that subject is submitted to any study procedure. All subjects for this study will be provided a consent form describing this study and providing sufficient information in language suitable for subjects to make an informed decision about their participation in this study. The person obtaining consent will thoroughly explain each element of the document and outline the risks and benefits, alternate treatment(s), and requirements of the study. The consent process will take place in a quiet and private room, and subjects may take as much time as needed to make a decision about their participation. Participation privacy will be maintained and questions regarding participation will be answered. No coercion or undue influence will be used in the consent process. This consent form must be signed by the subject and the individual obtaining the consent. A copy of the signed consent will be given to the participant, and the informed consent process will be documented in each subject's research record.

13.0 **References**

1. Hwang PS, and Willoughby DS. Mechanisms Behind Blood Flow–Restricted Training and its Effect Toward Muscle Growth. *The Journal of Strength & Conditioning Research*. 2019;33:S167-S79.
